4.3. Possible treatment groups

The study will include 35 participants. Initially, participants will be randomized in ratio 2: 2: 1 in groups G1: lower dose (1x10⁶ cells/by weight range), G2: higher dose (2x 10⁶ cells/by weight range) or G3: placebo, i.e. of the 35 participants, 14 will be randomized to the lowest dose group, 14 for the highest dose group or 7 for the placebo group. Thus, the groups listed below represent the groups in which participants can be included in the course of the study.

- **G1: Lower dose:** dose of 1x10⁶ cells/by weight range per administration.
- **G2: Higher dose:** dose of 2x10⁶ cells/by weight range per administration.
- **G3: Placebo:** constituted by the vehicle of the investigational product.

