The estimated number of participants was calculated considering clinical/regulatory and non-statistical assumptions. In this way, the document Considerations for the Design of Early-Phase Clinical Trials of Cellular and Gene Therapy Products - Guidance for Industry (FDA, 2015) predicts that a smaller sample size is considered appropriate for diseases considered fatal, where a major potential benefit may warrant an unknown risk. Additionally, considering conditions provided by the FDA document such as limited capacity of the investigational product manufacturing and the relatively rare prevalence of the target disease, Sponsor suggests the sample size of 35 participants, which is considered a feasible sample size and at the same time adequate to meet the proposed objective.

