#### 4. Endpoints

#### 4.1. Efficacy Endpoints

#### 4.1.1. Primary Efficacy Endpoint

The primary efficacy endpoint is rate of change (slope) per year from Baseline to V11 in total motor score (TMS) from the UHDRS.

Baseline is defined as the last non-missing value prior to first infusion at V0. If a value was not collected at V0 the nearest prior non-missing value is used as the Baseline value.

The TMS Score is the sum of the 31 items in the Motor Assessment portion of UHDRS with each item rated 0 to 4. The TMS is between 0 (Best) to 124 (Worst).

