#### 5. Statistical Hypothesis

This study is a Phase II study to determine efficacy and safety of Cellavita HD. Hypothesis tests for efficacy will be conducted as described below. No hypothesis testing will be performed on any safety data.

All hypothesis tests will be at the two-sided 5% significance level (Two-sided Type I error of 0.05)

H0: There is no difference in rate of change (slope) per year from Baseline through V11 in TMS between the two pooled active treatment groups and the placebo group

Ha: There is a difference in rate of change (slope) per year from Baseline through V11 in TMS between the two pooled active treatment groups and the placebo group

The following statistical tests will be performed:

- 1. Between the two active pooled treatment groups and placebo (primary)
  Participants receiving either 1 million or 2 million cells per kg (Treated) vs. Placebo
- Between each of the two active treatment groups individually and placebo (to determine efficacy of each treatment group compared to placebo)
   Participants receiving 1 million cells per kg (Treated) vs. Placebo
   And Participants receiving 2 million cells per kg (Treated) vs. Placebo
- 3. Between the two active treatment groups to assess similarity between the two treatment groups.

F-SA-06-01, Version 5.0/30 Dec 2021, SOPs Link: SOP-SA-06

Participants receiving 1 million vs. 2 million cells per kg.

The same tests performed for TMS will also be performed for other continuous endpoints.

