#### 7.4.1. Analysis on Primary Efficacy Endpoint

The primary efficacy variable for this study is the rate of change (slope) per year from Baseline to Visit 11 in TMS.

The null hypothesis represents no difference between the two active treatment groups pooled together as compared to the placebo group:

H0:  $\mu_A = \mu_P$ HA:  $\mu_A \neq \mu_P$ 

Where  $\mu_A$  is the mean rate of change (slope) per year from Baseline to Visit 11 in TMS for participants randomized to either of the two active doses and  $\mu_P$  is the mean rate of change (slope) per year from Baseline to Visit 11in TMS for participants randomized to the placebo group.

Analysis will be performed on observed data using MMRM. The model will include the following effects: Treatment, Baseline TMS, Treatment \* Day interaction. Due to the small sample size of the study and the study visits not conducted as per schedule of assessments due to COVID-19, the model may be changed or alternative models analyzed.

The unstructured covariance matrix for repeated observations within participants will be used. If the model does not converge, then a simpler covariance structure with less parameters will be used, according to the following order:

- 1. Toeplitz with heterogeneity (TOEPH)
- 2. ARH(1),
- 3. CSH,
- 4. Toeplitz (TOEP)
- 5. AR(1), and
- 6. CS.

The least square mean and standard error of the least square mean for each treatment group, and the 95% CI for the comparisons will be presented at each post-baseline visit.

In addition, actual observed values and rate of change (slope)s per year from Baseline to V3, V7 and V11 will be summarized using descriptive statistics for continuous data.

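### The fallback covariance list for the primary TMS slope test omits a random-slope model, so its later steps can misstate the standard error of the slope difference

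*SAP*

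**What the plan says.** SAP 4.1.1 sets the endpoint: "The primary efficacy endpoint is rate of change (slope) per year from Baseline to V11 in total motor score (TMS) from the UHDRS". SAP 7.4.1 gives the fixed part of the model: "The model will include the following effects: Treatment, Baseline TMS, Treatment \* Day interaction". The treatment-by-day term carries the slope comparison. The first-choice covariance is unstructured. After that: "If the model does not converge, then a simpler covariance structure with less parameters will be used, according to the following order". The order is TOEPH, ARH(1), CSH, TOEP, AR(1), CS.

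SAP 7.4.1 names no random intercept or slope, no sandwich standard error and no small-sample degrees-of-freedom method. It keeps the freedom to alter the model because of the small sample and COVID-19 visit disruption, but gives no criterion and no replacement.

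It does not say which visits enter. The UHDRS is done at every visit (Protocol 7.2.5), and least-squares means are to be shown at each post-baseline visit, which points to V1 to V11. The descriptive slopes are for V3, V7 and V11 only.

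On error rate, SAP 5 says: "All hypothesis tests will be at the two-sided 5% significance level (Two-sided Type I error of 0.05". On numbers, Protocol 4.3 says: "14 will be randomized to the lowest dose group, 14 for the highest dose group or 7 for the placebo group". The primary contrast is therefore 28 against 7.

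**The concern.** If people decline at different rates, the variance of a difference in mean slopes has two parts: measurement noise around each person's line, and the spread of the personal slopes. The second part does not shrink when more visits are added. A covariance model for a slope test has to represent it.

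CS and CSH assume one constant correlation between all pairs of visits, so they treat most of the slope spread as independent visit noise. ARH(1) and AR(1) read a stable person level plus rating noise as a decaying serial process. This tends to inflate the slope SE when slope spread is modest relative to noise. TOEPH and TOEP have a free correlation at each lag and pick up most of the slope spread.

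The primary p-value could therefore depend on which structure happens to converge. An SE that is too small risks a false claim of efficacy; one that is too large risks missing a real effect. SAP 7.4.2 uses the same model for the continuous secondary endpoints, and SAP 5 repeats the tests for the separate dose contrasts.

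**Working it through.** **No figure to reproduce.** The documents state no power, SD or standard error. On the sample size, SAP 3 says: "The estimated number of participants was calculated considering clinical/regulatory and non-statistical assumptions". The SDs below are assumptions.

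**Parameter counts, 11 post-baseline visits.**
- Unstructured: 11 × 12 / 2 = 66
- TOEPH: 11 + 10 = 21
- ARH(1) and CSH: 11 + 1 = 12 each
- TOEP: 1 + 10 = 11
- AR(1) and CS: 2 each

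With three visits the unstructured matrix needs 3 × 4 / 2 = 6.

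**Assumed truth.** Each person has an intercept (SD 4), a slope (SD s_b, 3 to 8 points per year) and independent visit noise (SD s_e, 2 to 4), conditioned on a baseline measured with the same noise. Visits fall exactly on days 30, 60, …, 330. Data are complete.

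**Method.** Let V be the true covariance, W the closest member of a listed family (Kullback-Leibler), X the intercept and time columns, and A = (X'W⁻¹X)⁻¹. The model-based slope variance is the slope element of A. The true variance of the same estimator is the slope element of A X'W⁻¹VW⁻¹X A. The ratio r is the square root of the first over the second. The group-size factor (1/28 + 1/7) cancels. Type I error = 2 × P(t₃₃ > 2.035 r), with 35 − 2 = 33 df.

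**CS by hand.** Here the ratio has a closed form. With T visits and Sxx the sum of squares of time in years,
- true variance per person = s_e²/Sxx + s_b²
- CS variance per person = s_e²/Sxx + s_b²/(T − 1)

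So with 11 visits CS counts one tenth of the slope variance. Sxx = 110 × (30/365.25)² = 0.742.
- s_b = 3, s_e = 4: √[(21.56 + 0.90)/(21.56 + 9)] = 0.86
- s_b = 4, s_e = 3: √[(12.13 + 1.6)/(12.13 + 16)] = 0.70
- s_b = 8, s_e = 2: √[(5.39 + 6.4)/(5.39 + 64)] = 0.41; 2.035 × 0.41 = 0.83, type I error about 41%

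For V3, V7 and V11, Sxx = 2 × (120/365.25)² = 0.216. The last setting gives √[(18.53 + 32)/(18.53 + 64)] = 0.78, an SE 22% too small.

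**All structures, V1 to V11, large-sample, in SAP order.**

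| Structure | Model SE / true SE | Type I error at nominal 5% |
|---|---|---|
| TOEPH (1st), TOEP (4th) | 0.81–0.99 | about 5–11% |
| ARH(1) (2nd), AR(1) (5th) | 0.90–1.37 | about 1–8% |
| CSH (3rd) | 0.56–0.87 | about 9–26% |
| CS (6th) | 0.41–0.86 | about 9–41% |

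At a ratio of 1.37, a test meant to have 80% power has about 55%: 1.37 × 1.96 = 2.69, against 1.96 + 0.84 = 2.80, and P(Z > −0.11) is about 0.55.

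**Sensitivity to the assumed SDs.** With person SD 10, slope SD 2 to 8 and noise SD 2 to 5, the ratios were: CS 0.41–0.95, CSH 0.56–0.95, ARH(1) 0.91–1.61, AR(1) 0.97–1.61, TOEPH 0.82–1.00, TOEP 0.88–1.00.

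**Finite-sample check.** REML simulation, 28 v 7, 11 visits, person SD 10, slope SD 4, noise SD 3, 400 runs, z critical values:

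| Structure | SE ratio | Type I error |
|---|---|---|
| TOEPH | 0.85 | 11% |
| ARH(1) | 1.18 | 2.5% |
| CSH | 0.66 | 20% |
| TOEP | 0.90 | 8% |
| AR(1) | 1.28 | 2% |
| CS | 0.65 | 20% |
| Unstructured, no small-sample correction | 0.68 | 18% |
| Random intercept and slope | 0.93 | 7.5% (6.5% on t with 33 df) |

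Simulation error is about 1 to 2 percentage points. The unstructured fit used a capped iteration and is approximate.

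**The case against.** **The first fallback is mild.** TOEPH comes first and absorbs most of the slope spread. CSH is reached only if the unstructured matrix, TOEPH and ARH(1) all fail; CS needs six failures. This stands, and the CS figures are not the expected result of a failed unstructured fit. TOEPH is not clean at this sample size, though (SE ratio 0.85 in simulation). The order also puts ARH(1) and CSH, with 12 parameters each, ahead of the better-behaved TOEP with 11.

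**Fallback may not happen.** Having 66 parameters for 35 people does not prove non-convergence. In a rough check outside SAS, the unstructured fit converged in 40 of 40 runs with complete data and 35 of 40 with 10% of visits missing. How often each step would be reached is unknown.

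**Only three visits may enter.** Then the unstructured fit needs 6 parameters, and no fallback errs by more than about 22%. The SAP does not settle this.

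**The response may be each person's own slope.** SAP 7.4.1 does say "The primary efficacy variable for this study is the rate of change (slope) per year from Baseline to Visit 11 in TMS", and on that reading a constant correlation would carry slope spread. But a response that is already a slope fits poorly with a treatment-by-day term.

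**The model may be changed anyway.** No replacement or trigger is named, so this adds discretion, not protection.

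**Equal spacing.** Toeplitz and AR structures assume equal spacing, and visits ran off schedule. The effect was not quantified. SAP 7.1 bases inference on nominal visits while SAP 4.1.2 uses actual days for slopes, so this is at most an ambiguity.

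**Conclusion.** The point holds in limited form. The primary test concerns slopes, and the fallback list leaves out the covariance model that matches a slope. With V1 to V11, the error is mild for TOEPH and TOEP. It can go either way for ARH(1) and AR(1), and is serious for CSH and CS if they are reached.

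A reader might infer more, and three stronger readings are not supported:
- That no listed structure captures slope variation, so any fallback is badly wrong. TOEPH and TOEP capture most of it.
- That ARH(1) and AR(1) always overstate the SE. The overstatement fades, and slightly reverses, when slope SD is large relative to noise (ARH(1) 0.91 and AR(1) 0.97 at slope SD 8, noise SD 2, person SD 10).
- That fallback is the likely route. This depends on which visits enter and on convergence, and the documents settle neither.

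Every size here depends on assumed SDs, complete data and a truth with linear individual courses. The directions for CS and CSH follow from their form; the amounts do not come from the documents. Convergence of the unstructured matrix does not by itself protect the test either: without a small-sample correction its simulated type I error was about 18%.

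**What to change.** Replace the six-step list with one fallback: a linear mixed model with random intercept and random slope in actual days since first infusion, independent residuals and Kenward-Roger degrees of freedom. If that fails, compare per-person least-squares slopes between pooled active and placebo in a baseline-adjusted linear model. Apply Kenward-Roger to the unstructured fit as well. State whether V1 to V11 or only V3, V7 and V11 enter the model.

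Under the assumed truth, which has the same form as this model, the large-sample SE ratio is 1.00. Simulated type I error was 6.2 to 7.0% with 11 visits and 3.7 to 4.8% with three, using t on 33 df (400 runs per setting). A separate simulation with 8,000 runs per setting gave 4.5 to 5.3%.

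The cost is one SAP paragraph and a small change to the PROC MIXED code. The downside is an assumption of roughly linear individual courses, which the slope endpoint already makes.

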#### 7.4.2. Analysis on Secondary Efficacy Endpoint

Continuous secondary efficacy endpoints will be analyzed as indicated above for the primary efficacy endpoint.

Categorical efficacy data will be analyzed using a Fisher's exact test.

Responder analysis may be performed using thresholds for responders using logistic regression. Covariates for logistic regression will include baseline value of the dependent variable

#### 7.4.3. Subgroup Analysis of Efficacy Endpoints

Since this is a small Phase 2 study elect subgroup analyses may be done based on severity of disease as measured by TFC or other efficacy endpoints, CAG repeats ( $< 44 \text{ vs} \ge 44$ ), Median CAP score, etc.

#### 7.5. Safety Analysis

#### 7.5.1. Treatment Compliance and Exposure

Exposure will be summarized by durations between each treatment and between first treatment and last treatment.

Dosing will be summarized by the number of syringes, duration of infusion and total volume at each visit.

#### 7.5.2. Adverse Events

Analysis of Adverse Events will be performed based on the safety population. All Adverse events will be coded using MedDRA ver. 24.1 Sept 2021

Statistical summaries will be performed on general incidence rate of treatment emergent adverse event (TEAEs) including number of events and number of participants with the events. In summarizing the number of participants with adverse events, if a participant has more than one event within the SOC (or PT) they will only be counted once in that row.

The terms Treatment Emergent Adverse Events (TEAEs) and Adverse Events (AEs) are used interchangeably below and unless otherwise specified refer to TEAEs.

Adverse Events will be summarized in the following Tables:

- Overall one page summary of TEAEs.
- Summary of TEAE's by SOC & PT sorted by total number of participants with the TEAE within a SOC and within SOC by total number of participants within a PT. This sort order will also be used in other Tables by SOC and PT indicated below.
- Summary of Severe TEAE's by SOC & PT.

- Summary of TEAE's by SOC, PT and Maximum Severity within SOC or PT. The order for displaying severity will be: Mild, Moderate, Severe.

- Summary of TEAE's Related to Study Drug by SOC PT. For this Table any AE's classified as Certain, Probable/Likely, Possible will be included.
- Summary of TEAE's by SOC, PT and Maximum Relationship to Study Drug within SOC or PT. The order for displaying Relationship to Study Drug will be: Conditional/Unclassified, Unlikely, Possible, Probable/Likely, Certain,.

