9.1.4. Causality categories: WHO-UMC System

a) Certain / Defined

- Event or alteration (abnormality) in laboratory examination with plausible temporal relationship in relation to the administration of the intervention. It cannot be explained by disease or other intervention or medicine;
- Response to discontinuation or plausible withdrawal (pharmacologically, pathologically);
- Event defined pharmacologically or phenomenologically (e.g., an objective and specific disorder or a pharmacologically recognized phenomenon);
 - Satisfactory re-exposure if necessary.

b) Probable

- Event or alteration (abnormality) in laboratory examination with a reasonable temporal relationship in relation to the administration of the intervention;
 - Unlikely to be attributed to a disease or other intervention, medicinal product;
 - Response to clinically reasonable discontinuation or withdrawal;
 - Re-exposure not required.

c) Possible

- Event or alteration (abnormality) in laboratory examination with a reasonable temporal relationship in relation to the administration of the intervention;
 - It can be explained by disease or other interventions, medicines;
- Information about withdrawal or discontinuation of treatment may be missing or obscure.

d) Improbable

- Event or alteration (abnormality) in laboratory examination that, in relation to the time of administration of the intervention, makes an unlikely (but not impossible) relationship;
 - Disease or other treatments provide plausible explanations.

e) Conditional / Unclassified

- Event or alteration (abnormality) on laboratory examination;
- More data is needed for an appropriate assessment, or;
- Additional data under investigation.

Source: The Uppsala Monitoring Centre - World Health Organization

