#### 4.2.2. Adverse Events

Adverse events are as defined in the protocol Section 9.1. Additional details on Serious Adverse Events (SAEs), classification of AEs according to expectation (unexpected, expected), Severity (Mild, Moderate, Severe,) and causality (Certain, Probable/Likely, Possible, Unlikely and Conditional/Unclassified) are defined in sections 9.1.1, 9.1.2, 9.1.3 and 9.1.4 respectively in the protocol.

Treatment Emergent Adverse Events (TEAEs) are all Adverse Events that started on or after the first administration of study drug.

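### The related-TEAE table omits events whose causality is still unresolved, and the SAP gives no explicit rule for ranking them in the maximum-relationship table

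*SAP*

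**What the plan says.** SAP 4.2.2 takes its causality grades from protocol 9.1.4. There are five: Certain, Probable, Possible, a fourth that the protocol calls Improbable and the SAP calls Unlikely, and Conditional/Unclassified. Neither document has an Unrelated grade. The protocol's entries for Conditional/Unclassified include "More data is needed for an appropriate assessment, or" and "Additional data under investigation". Judgement against a relationship has its own grade, Improbable.

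SAP 7.5.2 plans two tables that use causality:

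- The related-TEAE table by SOC and PT, for which "any AE's classified as Certain, Probable/Likely, Possible will be included".
- A second table, "Summary of TEAE's by SOC, PT and Maximum Relationship to Study Drug within SOC or PT", with this instruction: "The order for displaying Relationship to Study Drug will be: Conditional/Unclassified, Unlikely, Possible, Probable/Likely, Certain".

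For the table by maximum severity, the matching instruction is "The order for displaying severity will be: Mild, Moderate, Severe".

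SAP 7.2.1 allows no imputation of safety data beyond the medication-date rules and, where possible, shows missing data as a category. Neither document says how causality that is unresolved or missing at lock enters the related count.

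**The concern.** An event that nobody has yet been able to assess is handled, for the related-TEAE table, in the same way as an event assessed and judged unlikely to be due to the product. The first is an absence of judgement and the second is a judgement.

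The related-TEAE table matters here. Protocol 8.7.1.1.3 bases the safety assessment on reported adverse events in relation to causality. SAP section 5 tests no safety hypothesis, so the descriptive tables carry the safety conclusion. Protocol 9.5 says that the safety of mesenchymal stem cell therapy in general is not yet fully understood. With arms of 14, 14 and 7, moving one participant changes a percentage visibly.

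The second table needs a ranking before a maximum can be taken. The only order in the text puts Conditional/Unclassified at the low end, so an unresolved event can disappear behind an Unlikely one.

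**Working it through.** The plan states no figure on this point, so there is none to reproduce. The check applies the SAP's rules to example participants and then converts one participant into percentage points.

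**Inputs**

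- Related-table rule and category order: SAP 7.5.2.
- Meaning of the grades: protocol 9.1.4.
- Planned arm sizes of 14 low dose, 14 high dose and 7 placebo: protocol 4.3 and SAP section 3. Pooled active is 14 + 14 = 28. I assume that everyone randomised is treated as allocated.
- Number of participants with unresolved causality at lock: not given. I use 0 to 3 per group as an assumption.

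**Step 1: apply the rules within one SOC or PT row, reading the display order as ascending**

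| Participant's events in the row | In related table? | Shown in maximum-relationship table as | If Conditional/Unclassified ranked above Unlikely |
|---|---|---|---|
| Conditional/Unclassified only | No | Conditional/Unclassified | Conditional/Unclassified |
| Conditional/Unclassified and Unlikely | No | Unlikely | Conditional/Unclassified |
| Conditional/Unclassified and Possible | Yes | Possible | Possible |

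The related count can change only for participants in the first two lines: those with an unresolved event and none graded Possible or higher. Masking occurs only in the second line. Masking does not itself lower the related count, because neither event is in that table.

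**Step 2: size**

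If k affected participants in a group of n were counted as related, incidence would rise by 100 × k / n points.

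| Group | n | k = 0 | k = 1 | k = 2 | k = 3 |
|---|---|---|---|---|---|
| One dose arm | 14 | 0 | 7.1 | 14.3 | 21.4 |
| Pooled active | 28 | 0 | 3.6 | 7.1 | 10.7 |
| Placebo | 7 | 0 | 14.3 | 28.6 | 42.9 |

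**Step 3: the contrast with placebo**

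The rule applies to every arm. One affected participant in a dose arm and none in placebo would move the dose-minus-placebo difference by +1/14, or +7.1 points. One in each would move it by 1/14 − 1/7 = −1/14, or −7.1 points. The direction depends on counts that the documents do not give.

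**Step 4: does another provision close the gap?**

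- Protocol section 8 has inconsistencies resolved before analysis, and 8.8.5 describes final cleaning through queries. An event validly graded Conditional/Unclassified is not an inconsistency.
- Protocol 9.3 has the investigator clear up inconsistent evaluations. Its closing check by the monitor looks for events that have not recovered, not for open causality.
- Protocol 9.7 asks for enough detail to judge possible causality, but does not require a final grade.
- The missing-as-category rule in SAP 7.2.1 could display a missing grade, but would not put it into the related count.

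These provisions push towards resolution without requiring it before lock.

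**The case against.** The strongest reply is that nothing is concealed. Conditional/Unclassified is a level of its own in the maximum-relationship table. The events also appear in the overall TEAE summary, the SOC/PT table and the severity tables, none of which filters on causality, and SAP 7.1 lists all eCRF data. This stands. A reader might infer that unresolved events are being counted as unrelated, but the documents do not support that: there is no Unrelated grade and no unrelated count. The events are only left out of the related one.

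A second reply is that the SAP gives a display order, not a ranking. Where it means a ranking, in 7.5.3 and 7.5.4, it states an order for determining the worst value. This also stands in part: the ranking is an inference. It is a reasonable one, since the parallel severity order ascends and no other order is available for taking a maximum.

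A third reply is that counting an event that needs more data as related overrides the protocol's grade in the other direction, and that the separate level already planned is a defensible presentation. That is a fair reason to accept an additional row or sensitivity table in place of a changed main count. It does not justify leaving the related table with no account of unresolved events.

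Finally, the grade is provisional by definition, and there may be no such events at lock. That is possible, and nothing would then change.

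**Conclusion.** The point holds in a limited form. As written, the SAP leaves unassessed events out of the related-TEAE table alongside events judged Unlikely. The only order it offers for the maximum-relationship table would let an Unlikely event hide an unresolved one in the same row.

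If such events remain at lock, related-TEAE incidence may be understated by 7.1 points per affected participant in a dose arm, 3.6 in pooled active and 14.3 in placebo. This rests on the planned arm sizes, on an unknown number of affected participants, and on at least some of their events being truly related.

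A reader might go further and conclude that drug-related toxicity is understated, or that the comparison with placebo is biased in favour of the product. The documents support neither. They do not show that any unresolved event will remain, and the same rule applies to placebo. This is a minor correction to a stated tabulation rule.

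**What to change.** Amend SAP 7.5.2 as follows:

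1. Query every TEAE with Conditional/Unclassified or missing causality before database lock.
2. In the related-TEAE table, count any that remain as related. Alternatively, keep the present definition and add a row or sensitivity table that counts them as related. In either case, give the number of such events and participants by arm.
3. State that, in determining the maximum relationship, Conditional/Unclassified ranks above Unlikely and below Possible.
4. Use one name for the fourth grade, which is Improbable in protocol 9.1.4 and Unlikely in the SAP.

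The cost is a few lines of SAP text, one more row or table, and some query work. No new type of data is needed. The related-event rate may look slightly less favourable, and some events counted as related may later prove unrelated. Showing the count by arm lets the reader allow for that. If no such events remain, the tables do not change.
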